6.1 Randomisation method

The method of allocation sequence is minimisation.

Participants will be randomized individually in a 1:1 ratio to immediate vs. delayed start of GnRHa. Participants will be minimised based on four stratifying factors. These are birth registered sex (Male/Female), Tanner stage at entry (stage 2/3, stage 4/5), a diagnosis of a neurodevelopmental disorder or high levels of traits (yes/no) and site (7 levels). There will be an initial burn in of 10 participants who are simply randomised to provide an initial imbalance, where the minimisation can then work from. This means the initial participants are allocated to arms, irrespective of their stratifying factors.

6.2 Randomisation implementation

Allocation sequence generation

The randomisation sequence will be generated dynamically by the KCTU team via the KCTU web-based randomisation system, in accordance with the specification agreed with the CI and Senior Statistician. The Chief Investigator, Senior Statistician and TMG will be blinded to the sequence generation.

Enrolment of participants

Participants will be enrolled in the study for the purpose of CONSORT reporting at the point of signing a consent form to being screened for eligibility and will be part of the target N=226 at the point of randomisation.

Assignment of participants to interventions

Recruiting sites will assign participants to interventions by logging into the 'KCTU randomisation system' at www.ctu.co.uk (click 'randomisation' and select 'PATHWAYS study) and entering the participant's year of birth and age and stratifiers. The system will randomise the participants to active immediate or delayed in a ratio of 1:1.

Randomisation procedure

The Randomisation procedure will be provided in the site set up documentation.

6.3 Blinding status of researchers

Individual blinding status	Blinded	Unblinded
Chief Investigators	X	
Principal Investigators and all other staff at site		X
Co-applicants	X	
Trial Managers		X

The electronic version of this document is the latest version. It is responsibility of the individual to ensure that any paper material is the current version. Printed material is uncontrolled documentation.

Senior Trial Statistician	X	
Trial Statistician		X
Pharmacists at site		X
Outcome Assessors/Research Nurses		X
Treating clinicians		X
Programme Steering Committee (TSC)	X	
Data Monitoring Committee (DMC)		X

Table 3 - blinding status of PATHWAYS researchers

The blinding status of the research team is detailed in Table 3 above. Trial statistician will be initially blinded to complete the Statistical Analysis Plan, then will be unblinded to complete DMC reports.

*For roles not listed please refer to study delegation logs.

7 Data Management

7.1 Data Handling and Management

There are three datasets in PATHWAYS TRIAL: the Medrio EDC system dataset (including the Medrio ePRO dataset), the KCTU randomisation dataset, and the Q-Interactive dataset. A separate Medrio EDC Database will be developed for HORIZON INTENSIVE. The CI will act as custodian for all trial data.

Participant data will be pseudonymised using a study PIN generated by Medrio when a participant is registered on the system. All pseudonymised data will be stored on a password protected computer. Access to data held on electronic systems during the trial is restricted to delegated users at recruiting sites and key central staff including the Trial Manager(s), Clinical Research Associate, and Junior Statistician.

Physical source data, including signed consent forms, test results and other medical records should be filed at recruiting sites with the ISF, held in a secure location only accessible to delegated staff. The location of any physical personal data will be documented in the ISF and TMF.

Data Management Plans will be documented in the TMF, detailing relevant security information about the data system.

All essential documents will be archived in the TMF for 25 years following primary publication. Anonymised electronic research data will be backed up on an encrypted hard drive and stored in the TMF for archiving. As per GCP guidelines, identifiable research data will be archived in the ISF for a retention period of 25 years.

All data will be handled in accordance with the Data Protection Act (2018). All trial data will be stored in line with the Medicines for Human Use (Clinical Trials)

The electronic version of this document is the latest version. It is responsibility of the individual to ensure that any paper material is the current version. Printed material is uncontrolled documentation.

Amended Regulations 2006 and the Data Protection Act and archived in line with the Medicines for Human Use (Clinical Trials) Amended Regulations 2006 as defined in the Kings Health Partners Clinical Trials Office Archiving SOP.

Please refer to Appendix B for information on the flow of data throughout the current protocol.

7.1.1 Medrio EDC

A web based electronic data capture (EDC) system will be created in collaboration with the CI and trial analyst(s), using the Medrio system. This will be maintained by the King's Clinical Trials Unit (KCTU) and Medrio for the duration of the project. It will be hosted on secure servers by Medrio in the EU.

The CI or delegate (e.g., Trial Manager) will request email usernames and passwords from KCTU for new staff members joining the study and will request access removal when staff members leave the project. EDC access is strictly restricted through user-specific passwords to the authorised research team members. It is a legal requirement that passwords to the EDC are not shared, and that only those authorised access the EDC.

Site staff experiencing issues with the EDC system should contact the CI or delegate (e.g., Trial Manager). Medrio training videos are available at www.ctu.co.uk under 'Resources – Events & Training' tab.

Laboratory results may be reviewed directly in hospital laboratory systems where appropriate and need not be transcribed in full to the source data work. Any abnormal results must be recorded and transcribed in the EDC system as an adverse event. Normal results need not be transcribed.

The TM will provide Source Data Worksheets (SDWs) to recruiting sites following completion of database testing. Participating Sites will complete source data location lists defining the source data at their site.

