4.15 Laboratory Data

All tests listed below will be performed as per the time points indicated in the schedule of events in Table 2 (section 4.1). In addition, laboratory safety tests may be performed at unscheduled times, if deemed necessary by the PI and abnormal results recorded as an adverse event if clinically significant. Standard local NHS laboratories will be used to perform the tests at each trial site. If samples are requested elsewhere (eg via a community based doctor) the laboratory results report should be requested. Results must be printed and retained with the source data worksheets, after being reviewed and signed by a physician. Where the results indicate an adverse event or medical condition, this should be recorded in the medical history (at baseline) or on the adverse event log if occurring after randomisation.

Clinically significant abnormalities will be reported to the clinical team and discussed with the participant as necessary, as well as being recorded in the medical history form at screening and baseline or the adverse event form post-randomisation.

Individual result values will not be transcribed to the EDC system unless outside the normal range.

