4.15.1 Safety Bloods

4.15.1.1 *TRIAL Participants*

SCREENING AND BASELINE

All blood tests detailed below will be required at screening and baseline. A serum beta HCG will only be required at baseline to exclude early pregnancy prior to initiation of GnRHa.

Baseline blood tests will usually require anyone on contraceptive treatment (and other hormones as indicated) to have a washout period – where the hormones are not taken – prior to the blood test to ensure true basal hormone panel blood results are interpreted accurately. This will be a clinical decision that takes account of risk of becoming pregnant (and will consider the potential to move to other forms of contraception). The length of washout period is dependent on the type of medication the CYP is using and there may be some circumstances where a washout period is not required. The baseline blood test may need repeating if the washout period needs to be extended to show gonadal axis function. The length of washout period is

to be discussed with and determined by the expert endocrine panel. This panel consists of experienced paediatric endocrinologists from the UK and EU.

Screening blood tests do not require a washout period. Blood tests are to be repeated at the baseline visit if more than 3 months has elapsed since screening.

FOLLOW UP VISITS

At 6-monthly follow-up visits, the following blood tests are mandated: FSH, LH, Oestradiol, Testosterone, Renal Profile, Full Blood Count, Magnesium, Prolactin, Lipid and Bone Profiles. Additional blood tests may be ordered by the PI or SI where clinically indicated. These may include tests outside the standard panel, based on individual participant needs or emerging safety concerns.

HAEMATOLOGY

FULL BLOOD COUNT:

Haemoglobin Platelet count Total and differential leukocyte count
(neutrophils, lymphocytes, monocytes, eosinophils, basophils.) Haematocrit
Red blood cell count

BIOCHEMISTRY

RENAL PROFILE:

Sodium Potassium Creatinine Urea

LIVER PROFILE:

Alanine Transaminase (ALT) Aspartate Aminotransferase (AST) Alkaline
Phosphatase (ALP) Bilirubin Albumin Total Protein

LIPID PROFILE:

Total Cholesterol HDL LDL

BONE PROFILE:

Calcium Phosphate Parathyroid Hormone (PTH)

OTHER:

Ferritin Follicle Stimulating Hormone (FSH) Luteinising Hormone (LH)
Oestradiol Testosterone Prolactin Thyroid Stimulating Hormone
Free T4 Vitamin D

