13.1.7 Binary Physical Outcomes

- a) Adverse events
- b) Puberty staging (Tanner staging, both clinical and self-reported)

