Timepoint/Event	Screening (≤ 12 weeks to Day 0)	Baseline (Day 0)	Month 3 [+/- 2 weeks]	Month 6 [+/- 2 weeks]	Month 9 [+/- 2 weeks]	Month 12 [+/- 4 weeks]	Month 15 [+/- 2 weeks]	Month 18 [+/- 2 weeks]	Month 21 [+/- 6 weeks]	[+/- 2 weeks] Primary outcome Month 24	[+/- 8 weeks]	Ongoing*
Review of systems (history and examination)		X		X		X		X		X		
(Optional) Body Composition - Tanita Scale		X		X		X		X		X		
Telephone check-in			X		X		X		X			
Safety bloods	X	X		X		X		X		X		
***Pregnancy test (pocbp)++	X	X		X		X		X		X		
Urinalysis	X	X		X		X		X		X		
COGNITIVE MEASURES												
General Intelligence – WISC V		X				X				X		
Inhibition, shifting, verbal fluency – D-KEFS		X				X				X		
Memory: visual recognition, verbal recall - CHAMP		X				X				X		
Memory validity profile - MVP		X				X				X		
Executive functions at home - BRIEF		X				X				X		
MAGNETIC RESONANCE IMAGING (PATHWAYS CONNECT)												
Structural/functional Imaging – s/fMRI		X				X				X^^		
ONGOING												
***Adverse events log												X
***Concomitant medications log												X
Withdrawal form												X
PHARMACY												
Study medication dispensing/administration		X		X	X+++	X	X+++	X	X+++	X	X+++	

The electronic version of this document is the latest version. It is responsibility of the individual to ensure that any paper material is the current version. Printed material is uncontrolled documentation.

Timepoint/Event	Screening (≤ 12 weeks to Day 0)	Baseline (Day 0)	Month 3 [+/- 2 weeks]	Month 6 [+/- 2 weeks]	Month 9 [+/- 2 weeks]	Month 12 [+/- 4 weeks]	Month 15 [+/- 2 weeks]	Month 18 [+/- 6 weeks]	Month 21 [+/- 2 weeks]	Primary outcome Month 24 [+/- 8 weeks]	Ongoing*
Study medication dosing log											X
Legend			++ People of child bearing potential only +++ Dispensing at Months 9,15,21 if changing to 3 monthly preparation ^ Bone age scan at M12 & M24 optional ^^ Visit window for final scan of 6 weeks prior to/following final treatment injection ^^^Gender Identity Questionnaire completed only at baseline for Parents								

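### Sections 4.15 and 7.1.1 of the protocol conflict on when an abnormal laboratory result is an adverse event, and following 7.1.1 would inflate the adverse-event outcome, possibly unequally by arm

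*Protocol*

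**What the plan says.** Section 7.1.1 (Medrio EDC), on laboratory results: "Any abnormal results must be recorded and transcribed in the EDC system as an adverse event". It has no clinical-significance condition.

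Section 4.15 (Laboratory Data) is different. Its general sentence begins "Clinically significant abnormalities will be reported to the clinical team and discussed with the participant as necessary" and goes on to place these abnormalities on the adverse event form after randomisation. Out-of-range results as such are handled as values: "Individual result values will not be transcribed to the EDC system unless outside the normal range". The same filter appears for unscheduled tests: "abnormal results recorded as an adverse event if clinically significant".

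Section 13.1.7 lists "a) Adverse events" as a binary outcome of TRIAL. Section 13.5.2.2.1 analyses binary secondary outcomes with a logistic mixed model under the primary estimand, whose endpoint (13.5.1.1) is 24 months.

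Section 4.15.1 fixes the follow-up panel: "At 6-monthly follow-up visits, the following blood tests are mandated: FSH, LH, Oestradiol, Testosterone, Renal Profile, Full Blood Count, Magnesium, Prolactin, Lipid and Bone Profiles".

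In Appendix A, Table 4 (immediate arm) schedules safety bloods at months 6, 12, 18 and 24. Table 5 (delayed arm) schedules them at months 12, 18 and 24.

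**The concern.** For a result outside the range but not clinically significant, 7.1.1 requires an adverse event entry and 4.15 does not. This decides what sites put in the database, so an analysis plan written later cannot fully repair it. Sites that read different sections will log different things.

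Three consequences follow if 7.1.1 is applied as written. First, the adverse-event outcome fills with results of no clinical meaning, and a real difference between arms is diluted. Second, the rule produces events in proportion to blood draws. If the delayed arm has one draw fewer, the immediate arm shows an excess that owes nothing to the drug. Third, the panel includes LH, FSH, oestradiol and testosterone, which the drug is meant to lower. The protocol does not say whether a lowered value counts as abnormal for adverse event recording.

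**Working it through.** The protocol states no adverse event rate, abnormal-result rate or power for this outcome, so there is no figure of its own to reproduce.

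**Inputs from the protocol**
- Analytes per mandated follow-up draw (4.15.1): FSH, LH, oestradiol and testosterone 4; renal 4; full blood count 10; magnesium 1; prolactin 1; lipids 3; bone 3. Total 26.
- Post-randomisation draws: immediate 4 (Table 4), delayed 3 (Table 5). By month 12: 2 and 1.
- 226 participants at 1:1 (13.4.1, 6.1), so 113 per arm.

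**Assumptions**
- r, the chance that one test is out of range: 5% (a 95% reference range), 2.5% or 1%.
- k, the effective number of independent tests per draw: 26, or 10 to allow for correlated analytes.
- The outcome is any adverse event per participant.
- Clinically significant event rates as given below.
- A two-sided 5% comparison of two proportions stands in for the planned Bayesian logistic mixed model. It is rough when rates are close to 100%.

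**Step 1. At least one abnormal result over v draws:** q(v) = 1 − (1 − r)^(k·v). For example, 1 − 0.95^104 = 99.5% and 1 − 0.95^78 = 98.2%.

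| k | r | one draw | immediate, 4 draws | delayed, 3 draws |
|---|---|---|---|---|
| 26 | 5% | 74% | 99.5% | 98.2% |
| 26 | 2.5% | 48% | 92.8% | 86.1% |
| 26 | 1% | 23% | 64.8% | 54.3% |
| 10 | 5% | 40% | 87.1% | 78.5% |
| 10 | 2.5% | 22% | 63.7% | 53.2% |
| 10 | 1% | 10% | 33.1% | 26.0% |

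The expected number of entries does not depend on independence. At 5% it is 26 × 0.05 × 4 = 5.2 per immediate participant and 3.9 per delayed participant, or 113 × 9.1 ≈ 1,028 in all. At 1% it is 113 × 1.82 ≈ 206.

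**Step 2. Dilution.** With true rate p, the recorded rate is 1 − (1 − p)(1 − q). Power is Φ[(d − 1.96·SE₀)/SE₁], with d the difference between the two rates, SE₀ pooled and SE₁ unpooled. For assumed true rates of 40% v 22%: SE₀ = √(0.31 × 0.69 × 2/113) = 0.0615, SE₁ = √((0.24 + 0.1716)/113) = 0.0604, and power is Φ(0.98) = 84%. Adding one draw's background equally to both arms:

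| k, r | recorded rates | power |
|---|---|---|
| 26, 5% | 84.2% v 79.4% | 15% |
| 26, 1% | 53.8% v 39.9% | 55% |
| 10, 5% | 64.1% v 53.3% | 38% |
| 10, 1% | 45.7% v 29.5% | 72% |

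**Step 3. Spurious excess under Table 5.** True rate 10% in both arms, so any detected difference is false:

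| k, r | year 1 (2 v 1 draws) | detected | 24 months (4 v 3 draws) | detected |
|---|---|---|---|---|
| 26, 5% | 93.8% v 76.3% | 96% | 99.6% v 98.4% | 14% |
| 26, 1% | 46.6% v 30.7% | 69% | 68.4% v 58.9% | 31% |
| 10, 5% | 67.7% v 46.1% | 91% | 88.4% v 80.7% | 36% |
| 10, 1% | 26.4% v 18.6% | 29% | 39.8% v 33.4% | 17% |

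The 2.5% cases fall inside these ranges. Urinalysis, unscheduled tests and any flags for lowered hormones are left out; they would raise the recorded rates.

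**The case against.** A reader might infer that almost every participant will have an event and that the outcome will stop discriminating. The documents do not support that as a fact. They give no abnormal-result rate, and several analytes are linked (haemoglobin, haematocrit and red cells; total and differential leukocytes). The share with at least one abnormal result runs from about a quarter to nearly all. The protocol also does not say whether the binary outcome means any event, events by type or related events. That may properly be left to the analysis plan, and the power losses apply only to the first.

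A reader might also take the 96% false-detection figure as the trial's error rate. It belongs to a year-1 contrast at the least favourable inputs. Section 2.2 describes a midpoint comparison, but none is specified for adverse events, and the stated endpoint is 24 months, where the range is about 14% to 36%. The draw imbalance is itself disputed within the protocol: Table 2 shows month-6 bloods, 4.15.1 mandates them at 6-monthly visits, and 5.2.6 promises both arms the same monitoring.

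Nor is real harm simply hidden. Each event is graded for intensity and causality (9.2), serious events are reported separately within 24 hours, and safety bloods and bone density are outcomes in their own right (13.1.6). The definition in section 9, an untoward medical occurrence, leans towards 4.15. Whether suppressed hormones would be flagged is unknown, because no reference ranges are given.

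All of this limits the size. None of it removes the contradiction.

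**Conclusion.** The conflict between 4.15 and 7.1.1 holds as written and reaches a listed outcome. Its direction is clear: 7.1.1 adds events without clinical meaning and, if Table 5 is correct, more of them in the immediate arm.

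Its size rests on the assumed per-test rate (1% to 5%), the effective number of tests (10 to 26) and an any-event-per-participant outcome. On those assumptions, 33% to 99.5% of immediate and 26% to 98% of delayed participants would have at least one abnormal result. Power for an assumed 40% v 22% would fall from 84% to between 15% and 72% with one draw's background. With equal true rates of 10%, a false difference would be detected with probability 29% to 96% in year 1 and about 14% to 36% at 24 months. Should-fix.

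**What to change.** - Align the sentence in 7.1.1 (and the data management plan) with 4.15: an abnormal result goes on the adverse event log only when the investigator judges it clinically significant, and other out-of-range values stay as laboratory data.
- State how hormone values lowered by the drug's intended action are classified for adverse event recording.
- Reconcile Table 5 with Table 2, 4.15.1 and 5.2.6 on whether the delayed arm has month-6 bloods.

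The cost is a few sentences, best settled before sites enter data, because events logged under mixed rules would need reclassifying afterwards by people who know the allocation. The downside is that minor abnormalities leave the adverse event count; they remain in the laboratory data.

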7.1.1.1 Medrio ePRO

The web based Medrio EDC system will include ePRO (electronic Patient Reported Outcomes).

It is the responsibility of the site staff to ensure ePRO forms are complete at each timepoint for all participants (including where completion is In-Clinic, Remote or on Paper), as a high amount of missing data can render the study uninterpretable.

Authorised staff can check ePRO form completion by logging into their Medrio EDC account. Site staff will be responsible for following up participants who have not completed their ePRO forms before the end of each scheduled timepoint.

Where a participant wishes to withdraw from all further data collection for the study, staff should complete the EDC withdrawal form as soon as possible (i.e., on the

The electronic version of this document is the latest version. It is responsibility of the individual to ensure that any paper material is the current version. Printed material is uncontrolled documentation.

same day) to ensure the participant does not receive further notifications via the automatic ePRO scheduler.

No data will be entered via ePRO unless a participant has signed a consent form to participate in the trial.

The email address and/or telephone number may be entered into the Medrio ePRO system for completion of PROMs and data completion reminders, however as Protected Health Information (PHI) it will only be visible to necessary Medrio users as part of study operations, will be masked from those who do not require access to them, and will not form part of exported datasets.

There are 3 options for ePRO data entry described below:

1. In Clinic Data Entry by Participant:

After participant registration in the EDC, authorised staff can launch the relevant ePRO form(s) on a computer/smartphone/tablet and hand this to the participant for completion at the clinic visit.

2. Remote Data Entry by Participant (e.g., at home completion):

For 'Remote' ePRO (e.g., completion on a computer/smartphone/tablet at home), when the participant is registered in the EDC and their email address is entered by the authorised staff member, the participant will receive a 'Set Up Profile' notification email. The participant can follow the link in the email to set up their Medrio Profile and create a password.

A notification containing a link to the required ePRO form(s) will be sent to participants as per the pre-defined schedule. The participant will log in to their Medrio Profile, using their email address and password, to complete the active ePRO form(s) for that timepoint.

3. Data Entry by Site Staff if collected on Paper first:

If any ePRO forms are completed on paper instead, data entry users will transcribe these data into the EDC (as with any other non-ePRO forms) as soon as possible.

Paper ePRO forms used to transcribe into the EDC should be filed securely as source data in the Investigator Site File (ISF).

7.1.2 KCTU Randomisation System

A web-based randomisation system will be designed, using the bespoke KCTU randomisation system. The randomisation system will be created in collaboration with the trial analyst/s and the CI and maintained by the King's Clinical Trials Unit for the duration of the project. It will be hosted on a dedicated server within KCL.

The electronic version of this document is the latest version. It is responsibility of the individual to ensure that any paper material is the current version. Printed material is uncontrolled documentation.

Randomisation will be at the level of the individual using the method of minimisation stratified by: birth registered sex (male, female); tanner stage (stage 2/3, stage 4/5); diagnosis of a neurodevelopmental disorder or trait (yes, no); site (7-levels).

Randomisation will be undertaken by recruiting site staff, by authorised staff onto the randomisation system by going to www.ctu.co.uk and clicking the link to access the randomisation system. A full audit trail of data entry will be automatically date and time stamped, alongside information about the user making the entry within the system.

